13.4 Patients Lost to Follow Up

Patients who cannot be reached after at least three attempts will be categorized as lost to follow up. The attempts to reach the patients must be documented, with at least one of the attempts written and sent to the patient *via* certified or registered mail. Patients lost to follow up will still be included in the analysis of the study. For patients lost to follow up, the Investigator may check public records for survival status at 12 months.

14.0 STOPPING RULES

If the DSMB determines that continuation of enrollment in the trial provides an unreasonable risk to the patients, it may recommend study termination. All SAEs, regardless of attribution shall be reviewed by the DSMB.

In addition, adverse events attributable to the surgical procedure, such as intracranial infection, intracranial bleeding and seizures, shall be subject to review by the DSMB.

The DSMB shall be the final arbitrator for attributions.

15.0 CLINICAL AND LABORATORY EVALUATIONS AND PROCEDURES

15.1 Medical History

Medical history will include significant medical conditions and surgical history, medications taken within 2 weeks prior to signing the Informed Consent.

15.2 Physical Examination and Vital Signs

A complete physical examination will be performed (including a genital/rectal exam if clinically indicated).

Vital signs will include temperature, blood pressure at rest (while subject is in seated position), heart rate, and respiratory rate. Height and weight will be recorded at Visit 1: Screening only.

15.3 Safety Laboratory

All safety laboratory evaluations will be conducted at a central laboratory. At every sampling time point, approximately 15 mL of blood will be drawn for each of the hematology and serum chemistry panels.

The following laboratory evaluations will be performed:

- Hematology Panel: hematocrit, hemoglobin, WBC, platelet count, absolute lymphocyte count, absolute neutrophil count
- Serum Chemistry Panel: sodium, chloride, calcium, potassium, magnesium, creatinine, BUN, AST, ALT, alkaline phosphatase, and total bilirubin
- INR and APTT

15.4 Pregnancy Test: Serum or urine β-hCG

- Serum β -hCG at Screening (using same blood draw as for serum chemistry), Visit 8, and Visit 10
- Serum β -hCG or Urine β -hCG at Baseline

15.5 HLA typing and ApoE4 and BDNF Val66Met Genotyping

HLA typing (molecular) of each subject will be performed at baseline to allow exploratory analysis of degree of mismatch to SB623 with respect to both efficacy and safety.

Genotyping at the ApoE locus (i.e., to determine if patient is homozygous for ApoE4, E2 or E3, or if patient is heterozygous for E2/E3, E3/E4 or E2/E4) will be performed at baseline.

Assessment of whether BDNFVal66Met mutation is present (yes/no) will be performed at baseline.

A central laboratory will be utilized for sample storage and assay.

15.6 Serum Anti-HLA Antibodies

Anti-HLA serum antibody measurements will be made to monitor a possible humoral-mediated immune response. Blood samples will be taken at the intervals indicated in the schedule of assessments for measurements of serum anti-HLA antibodies using the Luminex assay. Assays will be done periodically on pooled samples. A central laboratory will be utilized for sample storage and assay.

15.7 PBMC Samples

At each timepoint that serum antibody samples are collected, an additional sample for PBMC will also be collected. A central laboratory will be utilized for sample storage.

15.8 Clinical TBI Evaluations

15.8.1 Screening

15.8.1.1 Glasgow Outcome Scale-Extended (GOS-E)

Subjects will require a GOS-E score of 3-6 (i.e. moderate or severe disability) at screening. Specific information on scoring using the GOS-E can be found in the publication.⁴⁴

15.8.1.2 Motricity Index

To ensure subjects have a defined motor deficit, an assessment of the subject's Motricity Index will be calculated at Screening for study eligibility purposes. Subjects will require both Motricity Index UE score of 10-81 (at least two scores less than 33 with one of these less than 25, and at least one score greater than 0), and/or a LE score of 10-78 (at least two scores less than 33 with one of these less than 33 with one of these less than 25, and at least one score greater than 0).

15.8.2 Study Endpoints

15.8.2.1 Fugl-Meyer Motor Scale (FMMS) Score

The FMMS score will be calculated at Baseline and Weeks 4, 12, 24 (primary), 36 and 48. The treatment group will be compared to the control group based on the mean change from baseline at each month.

15.8.2.2 Disability Rating Scale (DRS) Score

The DRS total will be calculated at Baseline and Weeks 4, 12, 24 (secondary), 36 and 48. The treatment group will be compared to the control group based on the mean change from baseline at each month. Specific information on scoring using the DRS can be found in the publication.⁴⁵

15.8.2.3 Action Research Arm Test (ARAT) Total Score

ARAT scores will be calculated at Baseline and Weeks 4, 12, 24 (secondary), 36 and 48. The treatment group will be compared to the control group based on the mean change from baseline at each month.

15.8.2.4 Gait Velocity

Gait Velocity on a standard 10 m walk will be calculated at Baseline and Weeks 4, 12, 24 (secondary), 36 and 48. The treatment group will be compared to the control group based on the mean change from baseline at each month.

15.8.2.5 NeuroQOL

Two Domains of the NeuroQOL will be assessed at Baseline and Weeks 4, 12, 24 (secondary), 36 and 48 using the Short Forms. The 2 subdomains are the Upper Extremity Function (Fine motor ADL) and Lower Extremity Function (Mobility). The treatment group will be compared to the control group based on the mean change from baseline in T Scores at each month.

15.8.2.6 Global Rating of Perceived Change from Baseline

This assessment will be performed at Weeks 4, 12, 24 (secondary), 36 and 48. It will be performed by both the subject (may be completed by caregiver) and a blinded efficacy assessment clinician (ideally the "assessment site efficacy assessor") who does not have access to patient study safety information, thereby maintaining the blind of the trial. Subjects and clinicians will be asked about perceived changes in the subject's motor function by comparing "how well they are doing compared to before the surgical procedure". The following 7-point Likert scale will be used:

- Score 7 = Much better
- Score 6 = A little better, meaningful
- Score 5 = A little better, not meaningful
- Score 4 = About the same
- Score 3 = A little worse, not meaningful
- Score 2 = A little worse, meaningful
- Score 1 = Much worse

15.9 Physiotherapy

Subjects will be instructed on of a set of exercises (cylinder grasp, thumb raise, stand and squat, walk) to be carried out at home every morning and afternoon and to indicate their performance in a patient diary during Screening and Weeks 4, 12, and 26. The patient's diary will be reviewed at the clinical site to ensure completeness.

15.10 Leg Activity Monitoring

Leg Activity Monitoring is mandatory in the US and Japan only. Bilateral ankle sensors will be worn by subjects throughout the study. The leg activity monitors will be dispensed at either the Screening or Baseline visit, and at least 2 weeks of baseline data will be required. Activity data will be downloaded at the clinical site and changes from Baseline in activity parameters will be calculated at Months 1, 3, 6, 9 and 12.

15.11 Imaging (MRI), Chest X-Ray, CT, and ECG

15.11.1 MRI

Magnetic Resonance Imaging (MRI) of the brain will be obtained using either a 1.5 or 3 Tesla MRI scanner. Each subject should have all scans conducted on the same scanner if possible (excepting those used for stereotactic planning and post-operative assessments, within 2 weeks of the surgery (implant/sham)). All MRI scans will include T1-weighted, dual echo, and FLAIR MRI. These images will be recorded in standard digital format (DICOM) for review.

On visits 2, 5, 6, and 10 post-contrast MRI will also be acquired. The post-contrast images will be acquired 5 minutes after the administration of the contrast agent. During this waiting period, Dynamic Susceptibility contrast MRI will be acquired for measuring tissue perfusion imaging. This

SanBio, Inc. additional acquisition does not increase the scan time.

Diffusion tensor imaging (DTI) is an MRI technique which characterizes the magnitude, anisotropy and orientation of the diffusion tensor, using the pulsed-gradient, spin echo pulse sequence with a single-shot, echo planar imaging (EPI) readout. DTI data will be obtained from the whole brain, at least 30 diffusion encoding directions and may be obtained using either a 1.5 or 3 Tesla MRI scanner.

15.11.2 Chest X-ray

Standard chest x-ray techniques will be performed according to the schedule described above.

15.11.3 CT Scans

Standard CT techniques will be performed according to the schedule described above.

15.11.4 Electrocardiograms

All ECGs will be obtained in the supine position, after the subject has been resting supine for at least 10 minutes. ECGs will be 12 lead with a 10 second rhythm strip. ECGs should be obtained prior to drawing blood samples. All attempts should be made to use the same ECG recorder for all visits within individual subjects. ECGs will be centrally read at a core lab according to established quality assurance procedures for inter/intra reader variability. ECGs will be reviewed, signed and dated by the Investigator listed on the Form FDA 1572 (MD or DO) after each ECG collection. The same Investigator should review all ECG reports for a given subject whenever possible.

15.12 Central Imaging Core Laboratory

A centralized imaging core laboratory will be used to review lesion at study entry, develop imaging acquisition protocols, and conduct imaging processing and analyses.

16.0 ADVERSE EVENTS

16.1 General Information

An **adverse event** (AE) is any untoward medical occurrence in a patient or clinical investigation subject enrolled in the study and that does not necessarily have a causal relationship with the study product or surgical procedure. An AE can therefore be any unfavorable and unintended sign, symptom, or disease temporally associated with the use of the study product or surgical procedure, whether or not considered related to the study product or surgical procedure. This includes any side effects, injury, toxicity, or sensitivity reaction, and may include a single symptom or sign, a set of related symptoms or signs, or a disease. An adverse event is also any laboratory abnormality judged to be clinically significant by the Investigator or Sub-investigator(s) that worsened compared to baseline.

Throughout the course of the study, every effort should be made to remain alert to possible adverse experiences. Patients should be encouraged to report adverse events spontaneously or in response to general, non-directed questioning.

With the occurrence of an adverse event, the primary concern is the safety of the patient. If necessary, appropriate medical intervention should be provided.

An AE **does not** include:

• Medical or surgical procedures (*e.g.*, surgery, endoscopy, tooth extraction, transfusion); the condition that leads to the procedure is an adverse event

Confidential and Proprietary

- Pre-existing diseases or conditions present or detected at the start of the study that do not worsen in severity or frequency
- Situations where an untoward medical occurrence has not occurred (*e.g.*, hospitalization for elective surgery, social and/or convenience admissions)
- Overdose of concomitant medication without any signs or symptoms

A Serious Adverse Event (SAE) is any adverse event that results in any of the following:

- death,
- life-threatening event,
- inpatient hospitalization or prolongation of hospitalization,
- a persistent or significant disability/incapacity or substantial disruption of the ability to conduct normal life functions,
- congenital anomaly/birth defect, or
- an event that may require intervention to prevent any one of the other outcomes listed above (based on medical judgment)

If the subject develops an adverse event during the post-surgical hospitalization, the adverse event should be assessed as non-serious UNLESS the adverse event prolonged the hospital stay [beyond Visit 5], or resulted in one of the other serious outcomes (e.g., life-threatening; required intervention to prevent permanent impairment or damage; other serious (medically important event).

A Product Technical Compliance (PTC) includes a failure or malfunction and any adverse reaction and/or any responses in recipients of manufacturers of human cells, tissues, and cellular and tissue-based products, regardless of manufactures, distribution, storage, or use/application.

An **Unexpected Adverse Event** is any AE that is not identified in nature, severity, or frequency in the current Investigator's Brochure or product information. Adverse events assessed as related to surgical procedure, and Clavien-Dindo Classification

(http://www.surgicalcomplication.info/index-2.html) Grade II or higher would be considered unexpected or unanticipated, unless such event has been previously reported and documented in the IB.

A **Suspected Adverse Reaction** is an AE for which there is a reasonable possibility that the study product or surgical procedure caused the AE. A reasonable possibility means there is evidence to suggest a causal relationship between the study product or surgical procedure and the AE.

A Serious and Unexpected Suspected Adverse Reaction (SUSAR) is any suspected adverse reaction to the study product or surgical procedure that is both serious and unexpected.

All SUSARs will be submitted as expedited reports to the applicable regulatory authorities/federal agencies. For this study, serious and unexpected AEs involving neurological deterioration, procedural complications, seizures, benign and malignant tumors and pregnancy will also be submitted as expedited reports, regardless of attribution.

16.2 Adverse Event Reporting Period

The adverse event reporting period for this trial begins upon Enrollment and ends 12 months after the administration of SB623.

All AEs (both serious and non-serious) and PTCs must be followed until resolution or until a stable clinical endpoint is reached. All measures required for AE management and the ultimate outcome of the AE must be recorded in the source document and reported to the Sponsor.

16.3 Recording of AEs

All AEs, regardless of severity, seriousness, or presumed relationship to the study product or surgical procedure, must be recorded using medical terminology in the source document and on the CRF. Events will be recorded at all study sites using standard terminology provided by the Sponsor or designate (*e.g.*, CRO), such as MedDRA terminology.

The WHO (World Health Organization) Standard Toxicity Criteria (STC) will be used to assist in categorizing and grading adverse events. A copy of the WHO STC will be provided in the study documents. Whenever possible, a diagnosis should be given when signs and symptoms are due to common etiology (*e.g.*, cough, runny nose, sneezing, sore throat, and head congestion should be reported as "upper respiratory infection").

16.4 Assessing Relationship of AE to Study Product or Surgical Procedure

The Investigator must record his/her opinion concerning the relationship of the AE to the study product and the surgical procedure on the Adverse Event CRF. Table 4 below provides guidance for assigning relationship to study product or surgical procedure.

	Surgical Procedure
Unrelated	No temporal relationship to study product or surgical procedure, or the presence of a reasonable causal relationship to another drug, concurrent disease, or circumstance and the adverse event (AE).
Unlikely	A temporal relationship to study product or surgical procedure, but no reasonable causal relationship between study product or surgical procedure and the AE.
Possibly	A reasonable causal relationship between the study product or surgical procedure and the AE. Information related to withdrawal of cell treatment/procedure was lacking or unclear.
Probably	A reasonable causal relationship between the study product or surgical procedure and the AE. The event responded to withdrawal of cell treatment/procedure. Re- challenge was not required.
Definitely	A reasonable causal relationship between the study product or surgical procedure and the AE. The event responded to withdrawal of the cell treatment/procedure, and recurred with re-challenge, when clinically feasible.

Table 4Relationship of Adverse Event to Administration of the Study Product or
Surgical Procedure

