uncontrolled congestive heart failure
20. Presence of craniectomy (without bone flap replacement)
or other contraindication to stereotactic surgery
21. Participation in any other investigational trial within 4
weeks of initial screening or within 7 weeks of study entry
22. Botulinum toxin injection, phenol injection, intrathecal
baclofen, or any other interventional treatments for
spasticity (except bracing and splinting) within 16 weeks of
the Baseline visit. (interventional treatment refers to
treatment done with special equipment which is typically
performed in a surgical or procedural type facility - this does
not apply to oral medications such as oral baclofen)
23. Ongoing use of herbal or other non-traditional drugs
24. Substance use disorder (per DSM-V criteria, including
drug or alcohol)
25. Contraindications to head CT or MRI
26. Pregnant or lactating
27. Female patients of childbearing potential unwilling to use an
adequate birth control method during the 12 months of the study
28. Any other condition or situation that the investigator believes may
interfere with the safety of the subject or the intent and conduct of
the study
29. Patients with allergic reactions to the ingredients of SB623, the
drugs used when administering SB623 or the drugs used in testing
(applicable for Japan only)

SanBio, Inc.	Confidential and Proprietary
Dosage, Mode of Administration, and Treatment	SB623 cells are provided as a 1-mL sterile cell suspension, containing $\geq 8 \times 10^6$ cells/mL, cryopreserved in CryoStor TM freezing media. Cells are provided in individual 2-mL Nalgene TM cryovials with screw caps.
Duration	 Cells to be administered stereotactically only once through one burr-hole craniostomy within and adjacent to the injured area using 3 needle tracks and 5 cell deposits per track at varying depths (20 μL per deposit): 2.5 X 10⁶ SB623 Cells (8.3 X 10⁶ cells/mL) 5.0 X 10⁶ SB623 Cells (17 X 10⁶ cells/mL) 10.0 X 10⁶ SB623 Cells (33 X 10⁶ cells/mL)

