12.0 SAFETY ANALYSES

12.1 Adverse Events

All safety analyses will be performed on the safety population.

The summary of AEs will be limited to treatment emergent AEs, which are defined as any adverse event with onset on or after the initiation of treatment or any adverse event already present that worsens in intensity following exposure to study treatment.

The number and percentage of subjects with at least one adverse event, at least one serious adverse event (SAE), and at least one adverse event that led to discontinuation from the study will be presented. The number and percentage of subjects having an adverse event in each System Organ Class (SOC) and having each individual type of adverse event (Preferred Term) will be presented. Fisher's Exact Test will be used to test for differences between treatments (pooled SB623 vs. sham surgery) in the proportion of subjects experiencing AEs in each SOC. This analysis will also be performed for SAEs, except that no statistical testing will be performed. Adverse events will also be summarized at the event level by SOC/Preferred Term and severity, by SOC/Preferred Term and relationship to study product, by SOC/Preferred Term and relationship to surgery, and by SOC/Preferred Term and action taken.

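### Table 4 separates Probably and Definitely from Possibly by response to withdrawal, which has no meaning after a one-time implant or completed surgery, so the degree of relatedness is compressed into Possibly

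*Protocol*

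**What the plan says.** The Protocol synopsis (Dosage, Mode of Administration, and Treatment Duration) fixes a single administration: "Cells to be administered stereotactically only once through one burr-hole craniostomy". Neither document describes removing, stopping or repeating the implant.

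Protocol 16.4 sets out how causality is graded. "The Investigator must record his/her opinion concerning the relationship of the AE to the study product and the surgical procedure", and "Table 4 below provides guidance for assigning relationship to study product or surgical procedure". The three upper rows of Table 4 each begin with a reasonable causal relationship and then add a condition:

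- Possibly: "Information related to withdrawal of cell treatment/procedure was lacking or unclear".
- Probably: "The event responded to withdrawal of cell treatment/procedure". Re-challenge is waived.
- Definitely: "The event responded to withdrawal of the cell treatment/procedure, and recurred with re-challenge, when clinically feasible".

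The grades are reported. Protocol 18.3 plans an event-level summary by relationship, and SAP Appendix A, 12.1 plans tables "by SOC/Preferred Term and relationship to study product, by SOC/Preferred Term and relationship to surgery". The SAP list of tables carries these as 14.3.1.5 and 14.3.1.6, with Japan versus Rest of the World versions as 14.3.1.8.3 and 14.3.1.8.4.

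**The concern.** The withdrawal and re-challenge wording suits a drug that can be stopped and restarted. Here the cells stay in the brain and the operation is over before most adverse events begin. If the only step from Possibly to Probably is a response to withdrawal, the scale has no usable way to say that one event is much more surely caused by the treatment or surgery than another.

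At stake is how the relationship tables are read. A reader who sees empty Probably and Definitely rows would take them as a finding about safety, when the definitions alone could produce them. The protocol shows that such grades are used for reassurance: section 4.2 describes the adverse events of the earlier stroke study as going no higher than possibly related to SB623. The documents do not say whether that study used Table 4, but a similar ceiling here could come from wording rather than from data.

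**Working it through.** No figure is stated on this point and no calculation applies. The check sets each row of Table 4 against single administration, and then against each place where relatedness is used.

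**Step 1. Can each grade be met once the implant or operation is complete?**

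| Grade | Causal test | Added condition | Can be met? |
|---|---|---|---|
| Unrelated | No link in time, or another reasonable cause | None | Yes |
| Unlikely | Link in time, no reasonable causal link | None | Yes |
| Possibly | Reasonable causal link | Withdrawal information missing or unclear | Yes, by default |
| Probably | Reasonable causal link | Response to withdrawal | No |
| Definitely | Reasonable causal link | Response to withdrawal, and recurrence on re-challenge where feasible | No; fails at withdrawal |

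So 5 − 2 = 3 grades remain usable. Of the three that express a reasonable causal link, 3 − 2 = 1 remains. The obstacle is the withdrawal clause. Re-challenge is waived for Probably and conditional on feasibility for Definitely, so by itself it blocks neither.

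**Step 2. Two illustrative events.** Take a bleed along the needle track seen on the post-operative CT, and a later symptom whose link to the surgery is reasonable but weak. Both pass the shared causal test. Neither has a withdrawal result. Both are graded Possibly.

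**Step 3. Where is relatedness used, and at what threshold?**

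- Expedited reporting (Protocol 16.1) rests on a reasonable possibility of causation: "A reasonable possibility means there is evidence to suggest a causal relationship between the study product or surgical procedure and the AE". No withdrawal condition appears.
- Extended follow-up (Protocol 8.2) starts at Possibly.
- The DSMB enrollment trigger (Protocol 8.1) needs two serious events with potential attribution to SB623.
- The DSMB reviews every serious event whatever its attribution and has the last word on attribution (Protocol 14.0).
- Serious events go to the safety monitor within 24 hours whether related or not (Protocol 16.5).
- The relationship tables (Protocol 18.3; SAP Appendix A, 12.1) summarize the recorded relationship.

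Only the last use is sensitive to the defect. A cut at Possibly or above would lose no event. A cut at Probably or above would tend to zero by construction, but neither document plans one, and neither says which grades count as related.

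**The case against.** A reader might infer that no adverse event can ever be graded Probably or Definitely, and that relatedness as a whole is understated. The documents do not support that, for these reasons:

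- Table 4 is guidance for an opinion, not a binding algorithm.
- The operation is staged, with slow injections on three tracks (Protocol 6.0). An event that resolves when the procedure is halted could be graded Probably.
- Possibly already demands a reasonable causal relationship, so clearly procedural events are not mixed with those that lack one; the latter go to Unlikely or Unrelated.
- No reporting, follow-up or DSMB rule needs a grade above Possibly.
- The main safety comparisons do not use attribution. SAP Appendix A, 12.1 compares incidence by system organ class between pooled SB623 and sham with Fisher's exact test, and SAP Appendix E, 8.0 tabulates subdural and parenchymal hematomas by treatment and visit. An excess of bleeds would show whatever grade was assigned.
- The content of the table shells and any CRF guidance or site training is not in the text, so it cannot be said that the top rows will be empty.

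All of this stands and limits the point to the degree of relatedness. It does not remove the point. Guidance that cannot be applied is still a fault: sites that follow the text and sites that set it aside will grade the same event differently, and the counts from about 30 sites are then hard to interpret.

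**Conclusion.** The point holds for the degree of relatedness. Table 4 uses a criterion that does not fit a single irreversible administration, so two of its three causal grades are practically closed for events arising after the implant or operation is complete. The by-relationship tables, including the Japan versus Rest of the World versions, would show few or no Probably or Definitely events for a reason unrelated to safety.

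The number of events affected cannot be given. It would be tempting to say that every event with a reasonable causal link is misgraded, but that assumes each would otherwise stand above Possibly, and nothing in the documents shows it. Nor do they support a reading that a safety signal is hidden: event capture, expedited reporting, DSMB review and the comparison with sham do not depend on the top grades.

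The conclusion assumes that investigators apply Table 4 as written. How sites actually used it is not in the documents.

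**What to change.** Rewrite the Possibly, Probably and Definitely rows of Table 4 so that each can be met after a one-time procedure. Grade by timing in relation to the surgery, by plausible mechanism or anatomical location, and by presence or absence of an alternative cause. Delete the withdrawal and re-challenge conditions from all three rows, and carry the same wording into any CRF guidance.

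If events have already been graded, leave the recorded grades alone. The addendum to the main SAP reports that interim results had been unblinded, so regrading now would be open to bias. Instead, footnote tables 14.3.1.5, 14.3.1.6, 14.3.1.8.3 and 14.3.1.8.4 to say that the use of Probably and Definitely was limited by the definitions and that few events in those rows is not evidence of weak causality.

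The cost is wording in the protocol and guidance, or a footnote. Sample size, endpoints and visits do not change. With new definitions some events may move to a higher grade, so the tables may look less favourable; the count at Possibly or above should stay the same as long as the shared causal test is kept.
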